5.4.5. Handling of Withdrawals

The primary reason for withdrawal from this trial will be recorded on the Study Status data collection form. Subjects will be encouraged to complete the Early Termination Visit. The Early Termination Visit procedures are listed in [Section 7.5](#).

Subjects who withdraw, or are withdrawn or terminated from this trial, or are lost to follow-up after signing the ICF, randomization, and receipt of study vaccine may be replaced to ensure each vaccine arm has at least 20 evaluable subjects, up to a total of 60 evaluable subjects. In order to be evaluable, a subject must receive the ChAd3-EBO-Z vaccine at Visit 1 and the booster vaccination of either ChAd3-EBO-Z, MVA-BN®-Filo, or placebo on Day 8 as determined by randomization.

Subjects who withdraw, or are withdrawn or terminated from this trial, or are lost to follow-up after signing the ICF and randomization but before receipt of study vaccine may be replaced.

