3.2. Study Outcome Measures

3.2.1. Primary

- Frequency and severity of solicited local and systemic reactogenicity from the time of study vaccine administration through 7 days post-vaccination.
- Frequency and severity of vaccine-related unsolicited adverse events (AEs) from the first study vaccination through 28 days post second vaccination.
- Frequency and severity of clinical safety laboratory AEs from the time of first study vaccination through approximately 28 days after the second vaccination.
- Frequency of Serious Adverse Events (SAEs) and vaccine-related Medically Attended Adverse Events (MAAEs) through 6 months post first vaccination.

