9. SAFETY EVALUATION

All safety analyses will be presented using the safety population. Any medical condition that is present at the time that the subject is screened will be considered baseline and not reported as an AE, unless it worsens in severity or increases in frequency during the study. When calculating the incidence of solicited and unsolicited adverse events (i.e., on a per subject basis), each subject will be counted once and any repetitions of solicited and unsolicited adverse events within a subject will be ignored; the denominator will be the number of subjects in the safety analysis population unless results are shown by dose in which case the denominator will be the number of subjects that received the respective dose.

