9.3.2. Unsolicited Adverse Events

Vaccine-related unsolicited AEs from the first study vaccination through 28 days post second vaccination will be coded by Medical Dictionary for Regulatory Activities (MedDRA®) for preferred term and system organ class (SOC) ([Table 27](#)). These AEs will be summarized as number and percentage of subjects reporting at least one event in each MedDRA® preferred term and SOC, cross tabulated by severity grade (none, mild, moderate, severe). Corresponding results for all unsolicited AEs will be presented by study arm as shown in [Table 28](#). A categorization by severity and vaccine-relatedness by study arm will be provided as provided in [Table 29](#). Subject-level unsolicited adverse events will be provided as shown in [Listing 10](#).

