14.3 Safety Data

14.3.1 Displays of Adverse Events

Table 23: Overall Summary of Adverse Events

	Study Arm 1 ChAd3+Placebo (N=X)		Study Arm 2 ChAd3+ChAd3 (N=X)		Study Arm 3 ChAd3+MVA-BN (N=X)		All Subjects (N = X)	
Subjects* with	n	n%	n	%	n	%	n	%
At least one local solicited adverse event	x	x.x	x	x.x	x	x.x	x	x.x
At least one systemic solicited adverse event	x	x.x	x	x.x	x	x.x	x	x.x
At least one laboratory adverse event	x	x.x	x	x.x	x	x.x	x	x.x
At least one vaccine-related unsolicited adverse event	x	x.x	x	x.x	x	x.x	x	x.x
Mild (Grade 1)	x	x.x	x	x.x	x	x.x	x	x.x
Moderate (Grade 2)	x	x.x	x	x.x	x	x.x	x	x.x
Severe (Grade 3)	x	x.x	x	x.x	x	x.x	x	x.x
At least one serious adverse event [†]	x	x.x	x	x.x	x	x.x	x	x.x
At least one vaccine-related medically attended adverse event [§]	x	x.x	x	x.x	x	x.x	x	x.x

N = Number of subjects in the Safety Population. *: Subjects are counted once for each category regardless of the number of events. [†]: A listing of Serious Adverse Events is included in Table 28. [‡]: As reported on the Adverse Event eCRF. [§]: All vaccine-related medically attended adverse events are included in Table 29.

14.3.1.1 Solicited Adverse Events**Table 24: Number and Percentage of Subjects Experiencing Solicited Events with 95% Confidence Intervals by Symptom, Dose, and Treatment Group**

Symptom	Post Dose 1 Study Arm 1,2,3 ChAd3 (N=X)*			Post Dose 2 Study Arm 1 ChAd3+Placebo (N=X)			Post Dose 2 Study Arm 2 ChAd3+ChAd3 (N=X)			Post Dose 2 Study Arm 3 ChAd3+MVA-BN (N=X)			Post Either Dose Study Arm 1 ChAd3+Placebo (N=X)			Post Either Dose Study Arm 2 ChAd3+ChAd3 (N=X)			Post Either Dose Study Arm 3 ChAd3+MVA-BN (N=X)		
	n	%	95% CI†	n	%	95% CI†	n	%	95% CI†	n	%	95% CI†	n	%	95% CI†	n	%	95% CI†	n	%	95% CI†
Any Symptom	x	x.x	x.x, x.x	x	x.x	x.x, x.x	x	x.x	x.x, x.x	x	x.x	x.x, x.x	x	x.x	x.x, x.x	x	x.x	x.x, x.x	x	x.x	x.x, x.x
Any Systemic Symptom	x	x.x	x.x, x.x	x	x.x	x.x, x.x	x	x.x	x.x, x.x	x	x.x	x.x, x.x	x	x.x	x.x, x.x	x	x.x	x.x, x.x	x	x.x	x.x, x.x
Elevated Oral Temperature	x	x.x	x.x, x.x	x	x.x	x.x, x.x	x	x.x	x.x, x.x	x	x.x	x.x, x.x	x	x.x	x.x, x.x	x	x.x	x.x, x.x	x	x.x	x.x, x.x
Feverishness	x	x.x	x.x, x.x	x	x.x	x.x, x.x	x	x.x	x.x, x.x	x	x.x	x.x, x.x	x	x.x	x.x, x.x	x	x.x	x.x, x.x	x	x.x	x.x, x.x
Malaise	x	x.x	x.x, x.x	x	x.x	x.x, x.x	x	x.x	x.x, x.x	x	x.x	x.x, x.x	x	x.x	x.x, x.x	x	x.x	x.x, x.x	x	x.x	x.x, x.x
Fatigue	x	x.x	x.x, x.x	x	x.x	x.x, x.x	x	x.x	x.x, x.x	x	x.x	x.x, x.x	x	x.x	x.x, x.x	x	x.x	x.x, x.x	x	x.x	x.x, x.x

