14.3.1.2 Unsolicited Adverse Events

Table 27: Number and Percentage of Subjects Experiencing Vaccine-related Unsolicited Adverse Events with 95% Confidence Intervals by MedDRA® System Organ Class and Preferred Term, and Treatment Group

MedDRA System Organ Class	MedDRA Preferred Term	Study Arm 1 ChAd3+Placebo (N=X)			Study Arm 2 ChAd3+ChAd3 (N=X)			Study Arm 3 ChAd3+MVA-BN (N=X)		
		n	%	95% CI†	n	%	95% CI†	n	%	95% CI†
Any SOC	Any PT	x	x.x	x.x – x.x	x	x.x	x.x – x.x	x	x.x	x.x – x.x
[SOC 1]	Any PT	x	x.x	x.x – x.x	x	x.x	x.x – x.x	x	x.x	x.x – x.x
	[PT 1]	x	x.x	x.x – x.x	x	x.x	x.x – x.x	x	x.x	x.x – x.x
	[PT 2]	x	x.x	x.x – x.x	x	x.x	x.x – x.x	x	x.x	x.x – x.x
[SOC 2]	Any PT	x	x.x	x.x – x.x	x	x.x	x.x – x.x	x	x.x	x.x – x.x
	[PT 1]	x	x.x	x.x – x.x	x	x.x	x.x – x.x	x	x.x	x.x – x.x
	[PT 2]	x	x.x	x.x – x.x	x	x.x	x.x – x.x	x	x.x	x.x – x.x

Note: N = number of subjects in the Safety Analysis Population.

This table presents number and percentage of subjects. A subject is only counted once per PT.

†: Based on Clopper-Pearson.

Table 28: Number and Percentage of Subjects Experiencing Any Unsolicited Adverse Events with 95% Confidence Intervals by MedDRA® System Organ Class and Preferred Term, and Treatment Group

MedDRA System Organ Class	MedDRA Preferred Term	Study Arm 1 ChAd3+Placebo (N=X)			Study Arm 2 ChAd3+ChAd3 (N=X)			Study Arm 3 ChAd3+MVA-BN (N=X)		
		n	%	95% CI†	n	%	95% CI†	n	%	95% CI†
Any SOC	Any PT	x	x.x	x.x – x.x	x	x.x	x.x – x.x	x	x.x	x.x – x.x
[SOC 1]	Any PT	x	x.x	x.x – x.x	x	x.x	x.x – x.x	x	x.x	x.x – x.x
	[PT 1]	x	x.x	x.x – x.x	x	x.x	x.x – x.x	x	x.x	x.x – x.x
	[PT 2]	x	x.x	x.x – x.x	x	x.x	x.x – x.x	x	x.x	x.x – x.x
[SOC 2]	Any PT	x	x.x	x.x – x.x	x	x.x	x.x – x.x	x	x.x	x.x – x.x
	[PT 1]	x	x.x	x.x – x.x	x	x.x	x.x – x.x	x	x.x	x.x – x.x
	[PT 2]	x	x.x	x.x – x.x	x	x.x	x.x – x.x	x	x.x	x.x – x.x

Note: N = number of subjects in the Safety Analysis Population.

This table presents number and percentage of subjects. A subject is only counted once per PT.

†: Based on Clopper-Pearson.

Table 29: Unsolicited Adverse Events by MedDRA System Organ Class and Preferred Term, Maximum Severity, Relationship, and Treatment Group

MedDRA System Organ Class	Preferred Term	Severity	Study Arm 1 ChAd3+Placebo (N=X)						Study Arm 2 ChAd3+ChAd3 (N=X)						Study Arm 3 ChAd3+MVA-BN (N=X)					
			Related		Not Related		Total		Related		Not Related		Total		Related		Not Related		Total	
			n	%	n	%	n	%	n	%	n	%	n	%	n	%	n	%	n	%

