Any SOC	Any PT	Any Severity	x	x.x	x	x.x	x	x.x	x	x.x	x	x.x	x	x.x	x	x.x	x	x.x	x	x.x
		Mild	x	x.x	x	x.x	x	x.x	x	x.x	x	x.x	x	x.x	x	x.x	x	x.x	x	x.x
		Moderate	x	x.x	x	x.x	x	x.x	x	x.x	x	x.x	x	x.x	x	x.x	x	x.x	x	x.x
		Severe	x	x.x	x	x.x	x	x.x	x	x.x	x	x.x	x	x.x	x	x.x	x	x.x	x	x.x
SOC 1	PT 1	Any Severity	x	x.x	x	x.x	x	x.x	x	x.x	x	x.x	x	x.x	x	x.x	x	x.x	x	x.x
		Mild	x	x.x	x	x.x	x	x.x	x	x.x	x	x.x	x	x.x	x	x.x	x	x.x	x	x.x
		Moderate	x	x.x	x	x.x	x	x.x	x	x.x	x	x.x	x	x.x	x	x.x	x	x.x	x	x.x
		Severe	x	x.x	x	x.x	x	x.x	x	x.x	x	x.x	x	x.x	x	x.x	x	x.x	x	x.x
	PT 2	Any Severity	x	x.x	x	x.x	x	x.x	x	x.x	x	x.x	x	x.x	x	x.x	x	x.x	x	x.x
		Mild	x	x.x	x	x.x	x	x.x	x	x.x	x	x.x	x	x.x	x	x.x	x	x.x	x	x.x
		Moderate	x	x.x	x	x.x	x	x.x	x	x.x	x	x.x	x	x.x	x	x.x	x	x.x	x	x.x
		Severe	x	x.x	x	x.x	x	x.x	x	x.x	x	x.x	x	x.x	x	x.x	x	x.x	x	x.x

N = Number of subjects in the Safety Population. For severity, a subject is counted once per preferred term and is summarized according to their highest severity. For vaccine-relatedness, a subject is only counted once per preferred term and is summarized according to their closest relationship.

14.3.2 Listing of Deaths, Other Serious and Significant Adverse Events**Table 30: Listing of Serious Adverse Events**

Adverse Event	Associated with Dose #	# of Days Post Associated Dose (Duration)	# of Days Post Dose the Event Became Serious	Reason Reported as an SAE	Severity	Relationship to Study Treatment	If Not Related, Alternative Etiology	Action Taken with Study Treatment	Subject Discontinued Due to AE	Outcome	MedDRA System Organ Class	MedDRA Preferred Term
Subject ID: , Treatment Group: , AE Number:												
Comments:												
Subject ID: , Treatment Group: , AE Number:												
Comments:												

Table 31: Listing of Vaccine-Related Medically Attended Adverse Events

Adverse Event	Associated with Dose No.	No. of Days Post Associated Dose (Duration)	Severity	Relationship to Study Treatment	If Not Related, Alternative Etiology	Action Taken with Study Treatment	Subject Discontinued Due to AE	Outcome	MedDRA System Organ Class	MedDRA Preferred Term
Subject ID: Treatment Group: AE Number:										
Comments:										
Subject ID: Treatment Group: AE Number:										
Comments:										

Table 32: Listing of Non-Serious, Unsolicited, Moderate or Severe Adverse Events

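### As footnoted, SAP Table 29 can place a subject in a Related cell at a severity that none of that subject's related events reached

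*SAP*

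**What the plan says.** SAP section 3.2.1 lists among the primary outcomes: "Frequency and severity of vaccine-related unsolicited adverse events (AEs) from the first study vaccination through 28 days post second vaccination".

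SAP section 9.3.2 introduces Table 29 with "A categorization by severity and vaccine-relatedness by study arm will be provided as provided in" that table and gives no counting rule of its own. The table is titled "Unsolicited Adverse Events by MedDRA System Organ Class and Preferred Term, Maximum Severity, Relationship, and Treatment Group". In each arm, the rows Any Severity, Mild, Moderate and Severe cross the columns Related, Not Related and Total. The mock-up has an Any SOC / Any PT block followed by blocks for single preferred terms.

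The footnote to Table 29 gives two rules:

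- Severity: "For severity, a subject is counted once per preferred term and is summarized according to their highest severity".
- Relationship: "For vaccine-relatedness, a subject is only counted once per preferred term and is summarized according to their closest relationship".

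SAP section 9 adds a general rule for incidence: "each subject will be counted once and any repetitions of solicited and unsolicited adverse events within a subject will be ignored".

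Table 23 has a line "At least one vaccine-related unsolicited adverse event" with Mild, Moderate and Severe rows beneath it, overall only. SAP section 9.3.2 also promises related events by preferred term and system organ class, cross-tabulated by severity, and points to Table 27. The Table 27 mock-up has no severity rows.

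**The concern.** A cell in a two-way table of severity by relationship reads as a statement about an event: a cell that is Severe and Related says that the subject had a severe event judged related. The footnote instead maximises each attribute separately. When a subject has more than one event in a row of the table, the two maxima can come from different events, and the cell then describes an event that the investigator did not report.

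The severity of vaccine-related unsolicited events is a primary outcome. Because the Table 27 mock-up lacks severity, Table 29 is the only tabulation of related events by preferred term and severity. A spurious entry there could also contradict Table 23, whose severity rows sit under related events only.

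**Working it through.** The plan states no figure on this point, so there is none to reproduce. The check applies the two footnote rules to concrete cases.

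**Inputs.** Three severity grades and two relationship categories (Table 29 mock-up); highest severity and closest relationship, once per preferred term (Table 29 footnote); one count per subject (SAP section 9); 20 subjects per arm (SAP Table 1; Protocol section 5.4.5, "each vaccine arm has at least 20 evaluable subjects").

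**Step 1: one subject.** Take a mild related event and a severe unrelated event under the same preferred term. Highest severity is Severe; closest relationship is Related.

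| Cell | Severity rule met | Relationship rule met | Actual event |
|---|---|---|---|
| Mild, Related | no | yes | yes |
| Moderate, Related | no | yes | no |
| Severe, Related | yes | yes | no |
| Mild, Not Related | no | no | no |
| Moderate, Not Related | no | no | no |
| Severe, Not Related | yes | no | yes |

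Only Severe, Related satisfies both rules, and no such event occurred. The real severe unrelated event drops out of the Not Related column.

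**Step 2: all two-event patterns.** There are 3 × 2 = 6 kinds of event, hence 6 × 7 / 2 = 21 unordered pairs, repeats allowed.

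- Both events with the same relationship: 6 + 6 = 12 pairs. The cell matches a real event.
- One of each, with the related event at least as severe: 6 pairs. The cell matches the related event.
- One of each, with the unrelated event more severe: 3 pairs (mild related with moderate unrelated; mild related with severe unrelated; moderate related with severe unrelated). The cell matches no event.

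Total: 12 + 6 + 3 = 21. All 3 mismatches overstate related severity and none understates it.

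**Step 3: effect of one subject.** With 20 in the arm, the Severe, Related cell goes from 0/20 = 0.0% (exact 95% CI 0 to 16.8%) to 1/20 = 5.0% (0.1% to 24.9%). Table 29 itself shows only n and %; the intervals are given for scale.

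**Step 4: the same subject under column-specific severity.** Mild under Related, Severe under Not Related, Severe under Total. Severe, Related returns to 0/20, and every entry describes something that happened.

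**Step 5: frequency.** The documents do not give the joint rate needed. The nearest figure is the 16.4% of adults with any unsolicited event in the ChAd3-EBO-Z group of the phase II studies (Protocol section 2.3.1). As an illustration for the Any SOC / Any PT row, assume that this rate applies here and that having a related event (probability p1) and having an unrelated event (p2) are independent. Then 1 − (1 − p1)(1 − p2) = 0.164. The product p1 × p2 is largest when p1 = p2 = 1 − √0.836 = 0.086, giving 0.0073, or 0.0073 × 60 = 0.44 subjects in the whole trial. The artefact also needs the unrelated event to be the more severe, so it would be rarer still. Both assumptions are open: this trial gives two doses with frequent visits, and events may cluster within subjects.

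**The case against.** The strongest reply is that the footnote never says how the inner cells are filled. Its severity rule might govern only the Total column and its relationship rule only the Any Severity row, with the inner cells programmed sensibly. That is possible, so it would be too strong to say that the table will report false events. But the SAP does not state this reading, and one count per subject under both rules leaves only the mismatched cell. On the kinder reading, the inner cells of a primary-outcome table have no rule and need the same footnote.

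Other points against also carry weight:

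- Both rules are written per preferred term. The row where unlike events could most easily combine, Any SOC / Any PT, has no stated rule.
- Within a preferred term, the subject needs two events under the same term with different relationships. Symptoms such as headache are solicited for 7 days after each vaccination, so in those windows they would not enter Table 29.
- The true pairing can be recovered. Tables 30 and 32 and Listing 12 show severity and relationship side by side, and Table 23 and Figures 5 to 8 show related events by severity. With about 60 subjects, a false cell is easy to find. A listing does not correct the count, however.
- The study tests no formal hypothesis (SAP section 5).

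A reader might infer that several subjects would be over-graded, or that safety decisions would be distorted. The documents support neither. No stated rate yields such a count, and the halting rules in Protocol section 9.5 act on reported related events rather than on Table 29.

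**Conclusion.** The point holds as a minor defect in a tabulation rule. Read literally, the Table 29 footnote can show a related event at a severity that no related event reached, always in the upward direction, and it can put Table 29 at odds with Table 23. This rests on taking both footnote rules together with one count per subject. In the Any SOC / Any PT row it further assumes that the per-term rule is carried over.

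One affected subject adds 5.0 percentage points to a cell in an arm of 20, and somewhat less if replacements enlarge the arm's safety population. Whether any subject will be affected is unknown. It does not follow that the primary safety conclusions are unreliable: the mechanism needs a particular combination of events, and the event-level displays would expose it.

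**What to change.** Replace the two footnote sentences with one rule per column, applied within each row of the table:

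- **Related:** the highest severity among the subject's related events in that row.
- **Not Related:** the highest severity among the subject's unrelated events in that row.
- **Total:** the highest severity over all the subject's events in that row.

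State that the same rule governs Any SOC / Any PT. Add that a subject may appear under both Related and Not Related, so that the two columns may sum to more than Total.

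The cost is one footnote and a small change to the table program. Data collection, populations and other displays are unaffected.

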14.3.3 Narratives of Deaths, Other Serious and Significant Adverse Events

Not included in SAP, but this is a placeholder for the CSR.

14.3.4 Abnormal Laboratory Value Listings (by Subject)**Table 33: Listing of Abnormal Laboratory Results - Chemistry**

Subject ID	Treatment Group	Sex	Age (years)	Planned Time Point	Actual Study Day	Laboratory Parameter (Units)	Result (Severity)	Relationship to Treatment	If Not Related, Alternate Etiology	Action Taken with Study Treatment	Subject Discontinued Due to Result?

Table 34: Listing of Abnormal Laboratory Results - Hematology

Subject ID	Treatment Group	Sex	Age (years)	Planned Time Point	Actual Study Day	Laboratory Parameter (Units)	Result (Severity)	Relationship to Treatment	If Not Related, Alternate Etiology	Action Taken with Study Treatment	Subject Discontinued Due to Result?

14.3.5 Displays of Laboratory Results

14.3.5.2 Hematology Results

Table 35: Laboratory Results by Parameter, Maximum Severity, Study Day, and Treatment Group – Any Hematology Parameter

Study Visit Day	Treatment Group	None				Mild				Moderate				Severe			Missing			
		N	n	%	95% CI [†]	n	%	95% CI [†]	n	%	95% CI [†]	n	%	95% CI [†]	n	%	95% CI [†]	n	%	95% CI [†]
Baseline (First Vaccination)	Study Arm 1, 2, 3 ChAd3 (N=X)*	x	x	x.x	x.x – x.x	x	x.x	x.x – x.x	x	x.x	x.x – x.x	x	x.x	x.x – x.x	x	x.x	x.x – x.x	x	x.x	x.x – x.x
Day 8 (Second vaccination)	Study Arm 1, 2, 3 ChAd3 (N=X)*	x	x	x.x	x.x – x.x	x	x.x	x.x – x.x	x	x.x	x.x – x.x	x	x.x	x.x – x.x	x	x.x	x.x – x.x	x	x.x	x.x – x.x
Day 8 Post-Second Vaccination	Study Arm 1 ChAd3+Placebo (N=X)	x	x	x.x	x.x – x.x	x	x.x	x.x – x.x	x	x.x	x.x – x.x	x	x.x	x.x – x.x	x	x.x	x.x – x.x	x	x.x	x.x – x.x
	Study Arm 2 ChAd3+ChAd3 (N=X)	x	x	x.x	x.x – x.x	x	x.x	x.x – x.x	x	x.x	x.x – x.x	x	x.x	x.x – x.x	x	x.x	x.x – x.x	x	x.x	x.x – x.x
	Study Arm 3 ChAd3+MVA-BN (N=X)	x	x	x.x	x.x – x.x	x	x.x	x.x – x.x	x	x.x	x.x – x.x	x	x.x	x.x – x.x	x	x.x	x.x – x.x	x	x.x	x.x – x.x
Day 22 Post-Second Vaccination	Study Arm 1 ChAd3+Placebo (N=X)	x	x	x.x	x.x – x.x	x	x.x	x.x – x.x	x	x.x	x.x – x.x	x	x.x	x.x – x.x	x	x.x	x.x – x.x	x	x.x	x.x – x.x
	Study Arm 2 ChAd3+ChAd3 (N=X)	x	x	x.x	x.x – x.x	x	x.x	x.x – x.x	x	x.x	x.x – x.x	x	x.x	x.x – x.x	x	x.x	x.x – x.x	x	x.x	x.x – x.x
	Study Arm 3 ChAd3+MVA-BN (N=X)	x	x	x.x	x.x – x.x	x	x.x	x.x – x.x	x	x.x	x.x – x.x	x	x.x	x.x – x.x	x	x.x	x.x – x.x	x	x.x	x.x – x.x
Day 29 Post-Second Vaccination	Study Arm 1 ChAd3+Placebo (N=X)	x	x	x.x	x.x – x.x	x	x.x	x.x – x.x	x	x.x	x.x – x.x	x	x.x	x.x – x.x	x	x.x	x.x – x.x	x	x.x	x.x – x.x
	Study Arm 2 ChAd3+ChAd3 (N=X)	x	x	x.x	x.x – x.x	x	x.x	x.x – x.x	x	x.x	x.x – x.x	x	x.x	x.x – x.x	x	x.x	x.x – x.x	x	x.x	x.x – x.x
	Study Arm 3 ChAd3+MVA-BN (N=X)	x	x	x.x	x.x – x.x	x	x.x	x.x – x.x	x	x.x	x.x – x.x	x	x.x	x.x – x.x	x	x.x	x.x – x.x	x	x.x	x.x – x.x
Max Severity Post Baseline	Study Arm 1 ChAd3+Placebo (N=X)	x	x	x.x	x.x – x.x	x	x.x	x.x – x.x	x	x.x	x.x – x.x	x	x.x	x.x – x.x	x	x.x	x.x – x.x	x	x.x	x.x – x.x
	Study Arm 2 ChAd3+ChAd3 (N=X)	x	x	x.x	x.x – x.x	x	x.x	x.x – x.x	x	x.x	x.x – x.x	x	x.x	x.x – x.x	x	x.x	x.x – x.x	x	x.x	x.x – x.x
	Study Arm 3 ChAd3+MVA-BN (N=X)	x	x	x.x	x.x – x.x	x	x.x	x.x – x.x	x	x.x	x.x – x.x	x	x.x	x.x – x.x	x	x.x	x.x – x.x	x	x.x	x.x – x.x

N = Number of subjects in the Safety Population

Note: The “Max Post Baseline” rows indicate the maximum severity experienced by each subject at any time point post baseline, including unscheduled assessments.

*: Subjects in treatment groups that received the same study product were jointly analyzed.

†: Based on Clopper-Pearson.

Generate this table for each hematology laboratory parameter: Absolute Neutrophil Count, Hgb (Decrease), Platelet (Decrease), Platelet (Increase), WBC (Decrease), WBC (Increase) and chemistry parameter: Any Chemistry Parameter, ALT (Increase), BUN, Creatinine (Increase), Potassium (High), Potassium (Low), Sodium (High), Sodium (Low).

Table 36: Laboratory Summary Statistics by Parameter, Study Day, and Treatment Group – Absolute Neutrophil Count (K/mcL)

Time Point	Treatment Group	N	Mean	Standard Deviation	Median	Min, Max
Baseline (First Vaccination)	Study Arm 1,2,3 ChAd3 (N=X)*	x	x.x	x.x	x	x, x
Day 8 (Second Vaccination)	Study Arm 1,2,3 ChAd3 (N=X)*	x	x.x	x.x	x	x, x
Day 8 Post-Second Vaccination	Study Arm 1 ChAd3+Placebo (N=X)	x	x.x	x.x	x	x, x
	Study Arm 2 ChAd3+ChAd3 (N=X)	x	x.x	x.x	x	x, x
	Study Arm 3 ChAd3+MVA-BN (N=X)	x	x.x	x.x	x	x, x
Day 22 Post-Second Vaccination	Study Arm 1 ChAd3+Placebo (N=X)	x	x.x	x.x	x	x, x
	Study Arm 2 ChAd3+ChAd3 (N=X)	x	x.x	x.x	x	x, x
	Study Arm 3 ChAd3+MVA-BN (N=X)	x	x.x	x.x	x	x, x
Day 29 Post-Second Vaccination	Study Arm 1 ChAd3+Placebo (N=X)	x	x.x	x.x	x	x, x
	Study Arm 2 ChAd3+ChAd3 (N=X)	x	x.x	x.x	x	x, x
	Study Arm 3 ChAd3+MVA-BN (N=X)	x	x.x	x.x	x	x, x
Max Severity Post Baseline	Study Arm 1 ChAd3+Placebo (N=X)	x	x.x	x.x	x	x, x
	Study Arm 2 ChAd3+ChAd3 (N=X)	x	x.x	x.x	x	x, x
	Study Arm 3 ChAd3+MVA-BN (N=X)	x	x.x	x.x	x	x, x

N = Number of subjects in the Safety Population.

Note: The “Max Post Baseline” rows indicate the maximum severity experienced by each subject at any time point post baseline, including unscheduled assessments.

*: Subjects in treatment groups that received the same study product were jointly analyzed.

Generate this table for each hematology laboratory parameter: Absolute Neutrophil Count (K/mcL), Hgb (g/dL), Platelet count (K/mcL), WBC (K/mcL) and chemistry parameter: ALT (unit/L), BUN (mg/dL), Creatinine (mg/dL), Potassium (mmol/L), and Sodium, (mmol/L).

Table 37: Laboratory Summary Statistics by Parameter, Study Day, and Treatment Group – Fold Change in Absolute Neutrophil Count (K/mcL) Relative to Pre-First Vaccination

Time Point	Treatment Group	N	Mean	Standard Deviation	Median	Min, Max
Day 8 (Second Vaccination)	Study Arm 1,2,3 ChAd3 (N=X)*	x	x.x	x.x	x.x	x.x, x.x
Day 8 Post-Second Vaccination	Study Arm 1 ChAd3+Placebo (N=X)	x	x.x	x.x	x.x	x.x, x.x
	Study Arm 2 ChAd3+ChAd3 (N=X)	x	x.x	x.x	x.x	x.x, x.x
	Study Arm 3 ChAd3+MVA-BN (N=X)	x	x.x	x.x	x.x	x.x, x.x
Day 22 Post-Second Vaccination	Study Arm 1 ChAd3+Placebo (N=X)	x	x.x	x.x	x.x	x.x, x.x
	Study Arm 2 ChAd3+ChAd3 (N=X)	x	x.x	x.x	x.x	x.x, x.x
	Study Arm 3 ChAd3+MVA-BN (N=X)	x	x.x	x.x	x.x	x.x, x.x
Day 29 Post-Second Vaccination	Study Arm 1 ChAd3+Placebo (N=X)	x	x.x	x.x	x.x	x.x, x.x
	Study Arm 2 ChAd3+ChAd3 (N=X)	x	x.x	x.x	x.x	x.x, x.x
	Study Arm 3 ChAd3+MVA-BN (N=X)	x	x.x	x.x	x.x	x.x, x.x
Max Severity Post Baseline	Study Arm 1 ChAd3+Placebo (N=X)	x	x.x	x.x	x.x	x.x, x.x
	Study Arm 2 ChAd3+ChAd3 (N=X)	x	x.x	x.x	x.x	x.x, x.x
	Study Arm 3 ChAd3+MVA-BN (N=X)	x	x.x	x.x	x.x	x.x, x.x

N = Number of subjects in the Safety Population.

*: Subjects in treatment groups that received the same study product were jointly analyzed.

Generate this table for each hematology laboratory parameter: Absolute Neutrophil Count (K/mcL), Hgb (g/dL), Platelet count (K/mcL), WBC (K/mcL) and chemistry parameter: ALT (unit/L), BUN (mg/dL), Creatinine (mg/dL), Potassium (mmol/L), and Sodium (mmol/L).

